A number of preliminary studies conducted by our group set the stage for this proposal(1). We have extensive experience performing environmental monitoring within Baltimore city and have found that the city has high levels of biologically active indoor PM. In our prior cohort study of 150 asthmatic children, the mean (\pm SD) indoor PM concentration for PM_{2.5-10} (coarse) was $17.4 \pm 21.1 \mu\text{g}/\text{m}^3$ and for PM_{2.5} (fine) was $40.3 \pm 35.4 \mu\text{g}/\text{m}^3$, both of which were significantly higher than the average ambient measurements made over the same time period ($10.3 \pm 21.0 \mu\text{g}/\text{m}^3$ and $12.4 \pm 6.2 \mu\text{g}/\text{m}^3$; $p < 0.01$ for both comparisons). Eighty-five percent of homes had indoor levels of PM_{2.5} exceeding the EPA limit for ambient pollution (2, 14). In addition, we found that this indoor pollution is associated with increased asthma morbidity. Specifically, each $10 \mu\text{g}/\text{m}^3$ increase in PM_{2.5-10} was associated with increases of 8% in the number of days of symptoms

[figure not shown]

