2. Pregnancy (as defined by a positive urine pregnancy test at screening of all women of child-bearing potential)
3. Planning to relocate residence or activity that necessitates travel away from home for prolonged period of time during the study period
4. Current use of an air cleaner in the home

2. Study Statistics

A. Primary outcome variable

The change in concentration of fine and coarse particulate matter (PM_{2.5} and PM_{2.5-10}) with the intervention of an air cleaner, compared to sham air cleaner.

B. Secondary outcome variables

1. Asthma control will be compared between the intervention and sham groups. This will include evaluation of changes in respiratory symptoms from self-reported diaries, asthma morbidity and asthma-related quality of life from questionnaires.

2. In addition, we will assess the effects of the intervention compared to the sham on other markers of asthma health. This includes lung function as measured by spirometry, and biomarkers of inflammation as measured in the blood and the lower airways via bronchoscopy.

3. Finally, we will assess the effects of the intervention compared to the sham on the indoor air nicotine concentration.

C. Statistical plan including sample size justification and interim data analysis.

We aimed to enroll 40 participants in this crossover design in order to detect with 80% power (and an alpha of 0.05) a 40% difference in PM concentrations between groups, accounting for an ultimate drop out/loss to follow up rate of approximately 10-15%. The estimate in sample size was based on a prior study from Butz et al. (18), which showed that a sample size of 77 participants was adequate to detect a 44% difference in PM concentrations between the intervention and control groups. [Note that over the course of the study, the planned sample size of 40 was not attained due to difficulties with recruitment. Only patients in the parent observational study willing to undergo bronchoscopies were recruited, resulting in a total of only 23 patients followed, with 2 lost to follow-up by the end of the study.]

A descriptive analysis will be performed with calculation of means, standard deviations, and medians for continuous variables and proportions for categorical variables. Bivariate analyses to assess differences before and after the intervention in each group will be conducted using t-tests or the Wilcoxon rank-sum test for continuous variables and χ^2 or Fisher's exact test for categorical variables.

Citations:

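### No analysis is named for the primary cleaner-versus-sham contrast: one general sentence offers t-tests or the unpaired rank-sum test, with no selection rule and no scale, in a crossover sized on a 40% difference

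*Combined protocol and SAP*

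**What the plan says.** All of the analysis text is in section 2 (Study Statistics), part C. After a line on descriptive statistics, one sentence covers inference. It concerns pre/post differences within each group, "using t-tests or the Wilcoxon rank-sum test for continuous variables". It applies to every continuous variable and gives no rule for choosing, no transformation and no pairing.

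The surrounding text describes something else:

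- Part A defines the primary outcome as the change in fine and coarse PM with the air cleaner, compared with sham.
- Study Procedures describes a two-period crossover and says that participants act as their own controls. No assessments are made during the washout.
- Part C sizes the trial to "detect with 80% power (and an alpha of 0.05) a 40% difference in PM concentrations between groups".
- Part C also carries a bracketed note: "Note that over the course of the study, the planned sample size of 40 was not attained due to difficulties with recruitment". It reports 23 followed and 2 lost by the end of the study.

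The only PM distribution figures are in the Background, "In our prior cohort study of 150 asthmatic children": mean 40.3 (SD 35.4) µg/m³ for fine PM and 17.4 (SD 21.1) µg/m³ for coarse PM.

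**The concern.** The one test sentence does not fit the primary question. It addresses change within each group, whereas the outcome is true against sham cleaner in the same home. It is also unclear what the pre-intervention measurement for the second period would be, since nothing is assessed during the washout.

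Of the two tests offered, rank-sum is a two-sample test and discards the pairing that the crossover was chosen to provide. The t-test is not described as paired. No scale is given, although the target is a percentage: a raw-scale t-test estimates a change in µg/m³, and a rank test yields no percentage.

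Two things are at stake. One is power, which is already short with 21 completers instead of 40 enrolled. The other is a conclusion that can turn on an unstated choice, in a document that already reports how follow-up ended.

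**Working it through.** **Inputs from section 2C.** Alpha 0.05 (taken as two-sided; not stated), power 80%, target ratio 1 − 0.40 = 0.60, 40 planned, losses of 10-15%. Completers: 23 − 2 = 21 pairs.

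**Inputs from the Background.** The means and SDs given above, from children's homes.

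**Assumed.** Within-home correlation ρ of 0.5, with 0.3-0.7 as the range and 0 and 0.9 as extremes; PM either lognormal or gamma. The documents give neither. In the simulations ρ is the correlation of the underlying normal scores.

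**Step 1: the plan's own figure.** "We aimed to enroll 40 participants in this crossover design", from an earlier air-cleaner trial "which showed that a sample size of 77 participants was adequate to detect a 44% difference in PM concentrations". The paired formula is n = (z_α/2 + z_β)² × 2(1 − ρ) × (SD/δ)², with (1.960 + 0.842)² = 7.85. At ρ = 0.5:

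- Fine, raw scale: δ = 0.4 × 40.3 = 16.12, so n = 7.85 × (35.4/16.12)² ≈ 38, or 43-45 after 10-15% losses.
- Coarse, raw scale: δ = 0.4 × 17.4 = 6.96, so n = 7.85 × (21.1/6.96)² ≈ 73, or 82-86.
- Fine, log scale: n = 7.85 × (0.756/0.511)² ≈ 18, or 20-22.
- Coarse, log scale: n = 7.85 × (0.951/0.511)² ≈ 28, or 32-33.

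The cited 77 can also be rescaled to a crossover, if it is taken as a total in two equal groups. On the raw scale 77 × (44/40)² = 93.2; on the log scale 77 × (ln 0.56/ln 0.60)² ≈ 99.2. Multiplying by (1 − ρ)/2 and allowing for losses gives about 36-41 at ρ = 0.3 and 26-29 at ρ = 0.5. So 40 can be reached, but only by assuming a scale and a correlation that the plan does not state.

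**Step 2: spread.** CV = 35.4/40.3 = 0.88 (fine) and 21.1/17.4 = 1.21 (coarse). For a quantity that cannot be negative this implies right skew, but it does not fix the shape. If PM is lognormal, log SD = √ln(1 + CV²) = 0.756 and 0.951. The effect is ln 0.60 = −0.511.

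**Step 3: power at 21 pairs, true 40% reduction, ρ = 0.5** (simulation, 6,000-8,000 trials per setting; %).

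| Test | Fine, lognormal | Coarse, lognormal | Fine, gamma | Coarse, gamma |
|---|---|---|---|---|
| Rank-sum (as named) | 57 | 34 | 32 | 12 |
| Unpaired t, raw | 47 | 25 | 40 | 16 |
| Signed-rank | 76 | 55 | 62 | 34 |
| Paired t, raw | 69 | 43 | 63 | 35 |
| Paired t, log | 83 | 65 | 55 | 26 |

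Signed-rank gains over rank-sum are 76 − 57 = 19 and 55 − 34 = 21 points (lognormal), and 62 − 32 = 30 and 34 − 12 = 22 points (gamma).

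**Step 4: dependence on ρ.** Over ρ = 0.3-0.7 with lognormal PM, rank-sum has 55-58% (fine) and 32-35% (coarse); signed-rank has 62-93% and 42-76%. With gamma PM, as ρ rises from 0.3 to 0.7, rank-sum falls from 35% to 31% (fine) and from 16% to 8% (coarse), while signed-rank rises from 50% to 83% and from 26% to 50%. At ρ = 0 (lognormal) pairing does not help: signed-rank 49% and 33%, rank-sum 55% and 38%.

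**Step 5: does the choice matter?** With a true 40% effect and ρ = 0.3-0.7, paired t and signed-rank disagree on significance in 8-13% (fine) and 14-19% (coarse) of lognormal trials, and in 7-13% of gamma trials.

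**Step 6: type I error.** With no effect and lognormal PM, taking the better of paired t and signed-rank gives 0.054-0.058 per fraction at 21 pairs. Taking the better of the two unpaired tests gives 0.002-0.031, because ignoring the pairing is conservative.

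**The case against.** The plan can be read generously. A t-test may be paired, and a t-test on logs is still a t-test, so the text is silent on both rather than excluding them. Part A speaks of change in concentration, and the Background reports symptom associations per 10 µg/m³, so an absolute change is a legitimate target. A 40% difference can also mean a ratio of arithmetic means. All of this stands. It is why the point is that nothing is fixed, and not that the plan commits to a wrong test.

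A reader might infer four stronger things, which the documents do not support:

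- *The missing log transform costs power.* This holds only if PM is close to lognormal. With gamma PM at the same CVs the log test is weaker than the raw paired t. Rank-sum on concentrations is unchanged by logs. The CVs come from an earlier cohort of children; these adults' homes may differ.
- *Neither named test could be right.* A paired t on a stated scale would be defensible.
- *Choosing between tests seriously inflates false positives.* Simulation gives about 11% for a hit on either fraction, but one fixed log test per fraction already gives about 9%. Most of that comes from testing two fractions.
- *The tests were chosen after the results were known.* The recruitment note is bracketed and in the past tense, while the analysis sentences are in the future tense. The note may have been inserted into older text. The documents date neither the analysis sentence nor any look at outcomes.

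**Conclusion.** The point holds in limited form. The primary contrast has no named analysis, no selection rule and no scale, and one of the two tests offered is unpaired in a crossover. That much is on the page.

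The most secure cost is the lost pairing: about 19-30 points of power at 21 pairs and correlation 0.5, under both shapes tried. It is smaller at lower correlation and absent at zero. The second cost is that the significance verdict depends on the choice of paired test in about 7-19% of trials with a true effect; the accompanying type I error is only about 5-6% per fraction. The case for a log scale rests on matching the 40% target. It does not rest on a guaranteed gain in power.

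The sizes depend on the child-cohort CVs and an assumed correlation. This should be corrected, but it does not invalidate the trial.

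**What to change.** In section 2C, for each PM fraction, name one primary analysis: the within-participant true-minus-sham difference in log mean concentration, reported as a ratio of geometric means (percentage reduction) with a 95% CI. List the Wilcoxon signed-rank test and the raw-scale paired difference as labelled sensitivity analyses, reported whatever they show. State the date on which this was fixed and whether anyone choosing it had seen outcome data. If it is fixed after follow-up ended, the SAP should say so.

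The cost is SAP wording; no new data are needed. There are two downsides. At correlation 0.5 the log analysis beats the raw paired t if PM is near lognormal (about 83% against 69% fine, 65% against 43% coarse), but it loses 63 − 55 = 8 points (fine) and 35 − 26 = 9 points (coarse) if PM is gamma-shaped. Zero or below-limit readings also need a stated substitution before logs are taken.
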